Smart Telehealth Exercise Intervention to Reduce COPD Readmissions

Study Protocol & Statistical Analysis Plan

NCT03089853

March 19, 2020

[name]., Principal Investigator
University of Alabama at Birmingham
Birmingham, AL 35294

We have designed a prospective *randomized controlled* study comparing an early NMES and telehealth remote pulmonary rehabilitation intervention with usual care to determine the impact on respiratory morbidity and also to investigate the mechanisms of such benefit. The primary outcome is the rate of all-cause readmissions within 30 days following an index hospitalization for COPD exacerbation. Secondary outcomes will include change in dyspnea, functional capacity, COPD disease activity and respiratory quality of life, and also changes in skeletal muscle and systemic inflammation.

Sample Size Calculation and Statistical Considerations: We propose enrolling a sample size of convenience of 30 participants randomized to intervention and usual care. We will use the observed effects size for the primary outcome of 30-day readmission to design a larger clinical trial. Standard deviations of measures of secondary outcomes will aid sample size calculations for Specific Aims 2 and 3. Comparisons between groups will be made for continuous variables using independent t-test or Mann-Whitney U-test for non-parametric data, and using chi-square or Fisher's exact test for categorical variables. Comparisons will be deemed to be statistically significant at a two-tailed alpha of 0.05 or less. Multivariable regression models will be created to assess association between the intervention and change in systemic inflammation and other measures such as functional capacity and quality of life indices, as well as muscle biopsy measures. The results of this pilot study will inform sample size for each Aim for a large mechanistic multicenter randomized controlled trial.

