Aim 1: To determine if an NMES and remote tele pulmonary rehabilitation intervention reduces 30-day all cause readmissions in patients hospitalized for acute exacerbation of COPD. All COPD patients hospitalized for an acute exacerbation will be enrolled in an ongoing comprehensive COPD care management intervention, and will be evaluated by a nurse or nurse practitioner in addition to the treating physician, and treated using a standardized order set which includes delivering a uniform duration of five days of antibiotics and systemic steroids. All participants will receive standardized care that includes educational material that encompasses general information about COPD, medications, and red flag symptoms; tobacco cessation counseling for smokers; short interval follow-up at 2 weeks at the COPD Clinic; monthly follow-up at the COPD Clinic; and regular phone calls by a registered nurse to enquire about symptoms as well as to address compliance with inhalers, smoking cessation, physical activity, nutrition, vaccines and coping with a chronic health condition. These calls will be made daily for 2 weeks and then weekly for 3 months. Deterioration in a patient's symptoms will be relayed to physicians for appropriate action. **Measurements:** Exacerbations and hospitalizations will be recorded.

Aim 2: To evaluate the effects of an NMES and remote tele pulmonary rehabilitation intervention on muscle strength, dyspnea and respiratory quality of life in COPD post hospital discharge. Pre and post intervention measurements will be made comparing assessments at 14 days at the time of COPD Clinic visit with assessments at 12 weeks on completion of the intervention. These measurements will be made in both intervention and control arms. **Instruments of Measurement:** (a) Muscle strength of quadriceps using a dynamometer (b) The 30-Second Chair Stand Test to assess skeletal muscle dysfunction, leg strength and endurance (c) Functional capacity using the six minute walk test (d) Physical activity using the Modified Baecke Questionnaire for Older Adults (e) Dyspnea using the San Diego Shortness of Breath Questionnaire and the modified Medical Research Council scores (f) COPD related Quality of life using the COPD Assessment Test (g) Forced expiratory volume in the first second (FEV₁) and (h) Psychosocial Risk Factor Survey (PRFS) to measure the primary psychosocial risk factors of depression, anxiety, anger/hostility, emotional guardedness and social isolation.

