Aim 3: To evaluate the effects of NMES and remote tele pulmonary rehabilitation intervention on systemic and muscle inflammation. Pre- and post- intervention assessments will be made of muscle and systemic inflammation at admission and at 4 weeks. **Instruments of Measurement:** (a) Muscle biopsy of the vastus lateralis muscle: Briefly, biopsies will be performed under local anesthetic (1% Lidocaine) using a 5 mm Bergstrom type biopsy needle under suction. Approximately 50-70 mg of muscle for immunohistochemistry will be mounted cross-sectionally and frozen in liquid nitrogen-cooled isopentane. Remaining tissue will be snap frozen in ~30 mg portions for biochemical assays. Myofiber type distribution will be assessed using myosin heavy chain (MHC) isoform immunofluorescence microscopy, muscle bioenergetics in response to oxidative stress, and protein cell signaling of the IL-6/STAT3 and TNF-alpha/NF-KB pathways by immunoblotting of muscle tissue protein lysate; (b) Systemic inflammation as assessed by serum C-reactive protein (CRP), serum fibrinogen, plasma TNF- α and plasma interleukin 6.

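### The 0.05 significance rule is not limited to the primary outcome, while Aims 2 and 3 list 17 to 21 unranked measures, so about one false positive is expected if the intervention does nothing

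*Combined protocol and SAP*

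**What the plan says.** The opening section of the combined protocol and SAP names a single primary outcome: "The primary outcome is the rate of all-cause readmissions within 30 days following an index hospitalization for COPD exacerbation". Its secondary outcomes are an unranked, open list of domains: "Secondary outcomes will include change in dyspnea, functional capacity, COPD disease activity and respiratory quality of life", together with muscle and systemic inflammation.

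The section on sample size and statistical considerations ties these measures to the later aims: "Standard deviations of measures of secondary outcomes will aid sample size calculations for Specific Aims 2 and 3". It then gives the tests in general terms: "Comparisons between groups will be made for continuous variables using independent t-test or Mann-Whitney U-test for non-parametric data", with chi-square or Fisher's exact test for categorical variables. The decision rule follows directly: "Comparisons will be deemed to be statistically significant at a two-tailed alpha of 0.05 or less". The next sentence adds multivariable regression models of the intervention for systemic inflammation, functional capacity, quality of life and muscle biopsy measures.

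The measures themselves are listed under Aims 2 and 3. The Aim 2 list runs from "a) Muscle strength of quadriceps using a dynamometer" to "h) Psychosocial Risk Factor Survey (PRFS) to measure the primary psychosocial risk factors of depression, anxiety, anger/hostility, emotional guardedness and social isolation". The Aim 3 list covers the muscle biopsy readouts and then "Systemic inflammation as assessed by serum C-reactive protein (CRP" and three further blood markers.

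The document nowhere gives a multiplicity adjustment, a testing order or a lead outcome for either aim, and it does not say that the results of Aims 2 and 3 are exploratory.

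**The concern.** A rule that declares significance at 0.05 controls error for one comparison. Applied to a long, unranked list, it makes a chance result likely, and the plan gives the reader no way to tell such a result from a real one. The study states an interest in mechanism as well as in readmission, and the mechanistic claims would rest on the Aim 3 measures, where nothing protects against chance findings. With about 15 participants per arm, only a large observed difference crosses 0.05, so a false positive would also look like a large effect.

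A second gap adds to this. For the measures that also go into a regression model, two analyses of the intervention effect will exist, and the plan does not say which one the conclusion rests on.

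**Working it through.** The plan states no family-wise error rate and no expected number of false positives, and its sample of 30 is one of convenience with no power calculation. There is therefore no figure of the plan's own to reproduce.

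**Count of measures**

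- Aim 2, items (a) to (g): quadriceps strength, chair stand, six-minute walk, physical activity, two dyspnea scores, COPD Assessment Test, FEV1 = 8.
- Aim 2, item (h), PRFS: 1 as a single score, or 5 if each named factor is compared.
- Aim 3, muscle: fiber type, bioenergetics, two signaling pathways = 4.
- Aim 3, blood: CRP, fibrinogen, TNF-α, interleukin 6 = 4.
- Total: 8 + 1 + 4 + 4 = 17, or 8 + 5 + 4 + 4 = 21.

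The count would rise if several fiber types, or several proteins within a pathway, were compared separately. The plan does not define the analysed variables closely enough to settle this.

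**Expected false positives if the intervention does nothing** (k × 0.05; no independence assumption needed)

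- k = 17: 17 × 0.05 = 0.85.
- k = 21: 21 × 0.05 = 1.05.

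**Chance of at least one, if independent** (1 − 0.95^k)

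- k = 17: 1 − 0.95^17 = 0.582.
- k = 21: 1 − 0.95^21 = 0.659.

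**Chance of at least one, if correlated.** The documents give no correlations, so a range is assumed. Simulated two-sided t-tests, 15 per arm, 21 normal outcomes with a common pairwise correlation and no true effect:

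| Pairwise correlation | Chance of at least one p ≤ 0.05 |
|---|---|
| 0 | 66% |
| 0.3 | 56% |
| 0.5 | 44% |
| 0.7 | 30% |

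Correlation lowers the chance of at least one false positive but leaves the expected number unchanged, because false positives then tend to occur together. Even at 0.7 the chance is 30/5 = 6 times the nominal 5%.

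**The case against.** The strongest reply is that this is a 30-person pilot with one named primary outcome. Its stated outputs for the larger trial are the observed effect on readmission and the standard deviations of the secondary measures, and a standard deviation does not depend on any alpha rule. That is correct, and it limits the harm. It does not remove the point: if estimation is the purpose, the significance rule for secondary comparisons is not needed, yet the plan sets it without restriction.

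It can also be said that psychosocial risk, FEV1 and physical activity are not among the secondary domains named at the start. That list is open, and the rule refers to comparisons rather than to labelled secondary outcomes. Leaving all three out of the lower count gives 17 − 3 = 14 measures, 14 × 0.05 = 0.70 expected false positives and 1 − 0.95^14 = 51% for at least one if independent. The conclusion is similar.

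A reader might infer several stronger things that the documents do not support:

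- That 21 is a minimum. It depends on comparing five PRFS factors separately; the survey is listed as one instrument, and the plan does not say how it will be scored.
- That every continuous outcome is tested twice at 0.05. The regression sentence gives examples, not a full list. It also comes after the 0.05 sentence, so applying the threshold to the models is a natural reading but not a stated one.
- That several tests will be run on each outcome and the best one chosen. The t-test and the Mann-Whitney test are stated as alternatives.
- That a chance secondary finding would decide whether or why the larger trial goes ahead. The plan says that the results inform sample size; no secondary p-value is a criterion for anything.
- That two in three is the likely chance of a false positive. The 66% needs independence, which is implausible for two dyspnea scales, factors of one survey and related inflammatory markers.

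**Conclusion.** The concern holds as a matter of inference on the secondary measures. The plan applies an unrestricted two-tailed 0.05 rule to group comparisons on 17 to 21 unranked measures, and it does not say which analysis is decisive where a regression model is added. With no true effect, about one false positive is expected. That figure rests on the count and on each test having a true size of 0.05, which is only approximate for discrete scores. The chance of at least one depends further on the correlation: 58% to 66% under independence, and about 30% to 56% for 21 measures at the assumed correlations of 0.7 to 0.3. The test of 30-day readmission is not affected. The harm is that isolated results on muscle, symptoms or inflammation may be read as established effects. A correction is worth making, but the point does not threaten the primary result.

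**What to change.** Limit the 0.05 significance statement to 30-day readmission. For Aims 2 and 3, state one analysis per outcome before any comparison by arm, including whether the simple group comparison or the regression model is the one reported and whether the PRFS is one score or five. Report the between-arm estimate with its 95% confidence interval, label these results exploratory, and use no significance wording for them.

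This suits the pilot's stated purpose better than a formal correction would. As an illustration, Bonferroni over 21 measures sets the threshold at 0.05/21 = 0.0024. For an assumed true difference of one standard deviation and 15 per arm, power by the normal approximation, Φ(√(15/2) − z), falls from Φ(2.74 − 1.96) = 78% to Φ(2.74 − 3.04) = 38%.

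The change needs SAP wording only and no new data. Its cost is that an isolated p-value below 0.05 among the measures of Aims 2 and 3 can no longer be claimed as a finding.

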Protocol/Intervention: Subjects with spirometry proven COPD and hospitalized for an acute exacerbation will be randomized in a 1:1 ratio to either receive remote tele pulmonary rehabilitation intervention or usual care. Usual care will consist of a protocolized regimen of 5 days of systemic steroids, unless the treating physician determines a different regimen, in which case the change will be documented. *NMES training protocol:* Bipolar self-adhesive neuromuscular stimulation electrodes will be placed over the distal-medial and proximal-lateral portion of the quadriceps femoris muscle group. Stimulation pulses (30 Hz trains of 300 μ sec biphasic pulses) will be delivered using a Respond II neuromuscular electrical stimulator (Medtronic, San Diego, CA). A 5 sec on/25 sec off work/rest ratio will be used initially, progressing to 10 sec on/30 sec off, as described by Neder.¹⁸ The patient will be fully supported while knee extensions are performed as the participant sits in a chair. Current from the stimulator will be manually increased and determined by patient tolerance. The goal for each patient will be to reach the highest tolerable amplitude (up to 100mA). Training will be performed on each quadriceps femoris muscle, 30 minutes/day, for 2 weeks including hospital stay till return to the COPD Clinic at which time participants will return the NMES equipment. *Remote Telehealth Intervention protocol:* On return to clinic for follow-up, patients will be initiated on remote telehealth pulmonary rehabilitation at home via a data enabled smart phone with video capabilities facilitating two-way conferencing, according to a standardized regimen for a total of 12 weeks. Safety will be monitored by also providing automatic sphygmomanometers to measure blood pressure before and after exercise, as well as heart rate and oxygen saturation assessments using a pulse oximeter. Exercise regimens will be prescribed thrice a week according to standard pulmonary rehabilitation guidelines.⁶⁶ Exercise sessions will include aerobic exercises, resistance training and breathing training techniques. Regimens will be individualized according to patients' baseline exercise tolerance as determined by initial six minute walk distance as well as their subjective sense of dyspnea. The study will have 3 aims as follows:

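### Change in CRP and IL-6 from an acute-illness admission sample has no stated scale or baseline adjustment; done as simple subtraction, it would mostly measure the admission value

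*Combined protocol and SAP*

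**What the plan says.** Under Sample Size Calculation and Statistical Considerations, the plan states that "Multivariable regression models will be created to assess association between the intervention and change in systemic inflammation". In the same section, continuous variables are compared between groups by "independent t-test or Mann-Whitney U-test for non-parametric data", and "Comparisons will be deemed to be statistically significant at a two-tailed alpha of 0.05 or less".

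Aim 3 fixes the times: "Pre- and post- intervention assessments will be made of muscle and systemic inflammation at admission and at 4 weeks". The blood markers are CRP, fibrinogen, TNF-alpha and IL-6. The Subjects section enrols within 36 hours of admission for an acute exacerbation. Aim 1 puts all participants on an order set with five days of antibiotics and systemic steroids.

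On size: "We propose enrolling a sample size of convenience of 30 participants randomized to intervention and usual care", in a 1:1 ratio, so about 15 per arm. The SDs of the secondary outcomes are meant to help size a larger trial for Aims 2 and 3.

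The plan names no transformation, percent change, ratio or covariate list. It neither plans nor excludes adjustment for the admission value.

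**The concern.** The first sample is taken in acute illness and the second after treatment, so a marker that peaks in an exacerbation should fall in both arms. If it is also right-skewed, the spread of admission values on the raw scale can be many times the spread at 4 weeks. The difference between the two is then dominated by how ill the patient was on admission, which treatment cannot affect.

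Mann-Whitney does not repair this when it is applied to change. Ranking comes after subtraction, so it ranks mainly the admission values.

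Low power alone would be a weak complaint about a convenience sample of 30. The larger stake is what the pilot hands on. An SD of raw change would describe admission severity more than the noise around the treatment comparison, and a Mann-Whitney p-value supplies neither an effect size nor an SD.

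**Working it through.** The plan states no power, effect size or SD for these markers, so there is no figure to reproduce.

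**Inputs from the documents:** 30 participants, 1:1, hence 15 per arm; two-sided 0.05; samples at admission and 4 weeks.

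**Assumed inputs:** log-normal markers; 4-week level halved in the intervention arm; log-scale correlation r between visits of 0.3-0.6; two cases for peak and spread. Case A has a 6-fold median fall with log-SD 1.2 at admission and 0.9 at 4 weeks. Case B has a 2-fold fall with log-SD 0.8 at both.

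**Step 1: what raw change consists of.** For a log-normal with median m and log-SD s, the variance is m²·exp(s²)·(exp(s²) − 1). Set the 4-week control median to 1 and take case A with r = 0.3.
- Admission (m = 6, s = 1.2): 36 × 4.221 × 3.221 = 489, SD 22.1.
- 4 weeks (m = 1, s = 0.9): 2.248 × 1.248 = 2.81, SD 1.68.
- Covariance: 6 × exp(1.125) × (exp(0.324) − 1) = 7.07.
- SD of change: √(489.4 + 2.8 − 14.1) = 21.9.

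The SD of change is almost exactly the admission SD. The correlation of raw change with the admission value is −0.99 or stronger.

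**Step 2: the size of the signal.** A halving moves the 4-week mean by 0.5 × exp(0.405) = 0.75. On raw change that is 0.75/21.9 = 0.034 SD. On the log scale with the admission value as covariate, the residual SD is 0.9 × √(1 − 0.09) = 0.859, and the same halving is ln 2/0.859 = 0.693/0.859 = 0.81 SD.

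**Step 3: power by simulation, 15 per arm, true halving.** Ranges run over r = 0.3-0.6; simulation error is about 1 point.

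| Analysis | Case A | Case B |
|---|---|---|
| t-test, raw change | about 4% | 12-15% |
| Mann-Whitney, raw change | 5-6% | 16-21% |
| Raw change, admission value as covariate | 40-51% | 52-64% |
| Mann-Whitney, 4-week values | 48-50% | 58-59% |
| t-test, log change | 30-47% | 48-73% |
| Log 4-week value on arm and log admission value | 55-70% | 65-80% |

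The subtraction does most of the damage. Adding the covariate to raw change gains 36-47 points in case A (from 4% to 40-51%), and taking logs as well adds 15-19. This split depends on the order: log change without the covariate also recovers much of the loss. The combination is best in both cases.

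**Step 4: other assumed profiles** (same sequence of tests, without Mann-Whitney on 4-week values).
- Three CRP-like profiles (3-, 6- and 10-fold falls, log-SD 0.8-1.1): raw t-test 4-7%, Mann-Whitney 5-10%, raw change with covariate 31-51%, log change 31-45%, log model with covariate 47-66%.
- IL-6-like (10 to 4, log-SD 0.9/0.7, r = 0.4): 7%, 11%, 68%, 53%, 80%.
- TNF-like and fibrinogen-like (log-SD 0.22-0.4, small fall): raw-change tests 85-100%, all others about 100%.

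With no treatment effect, all tests rejected in 3.4-5.7% of trials, so the differences are not due to inflated error rates.

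**Step 5: consequence for the next trial.** For 80% power, n per arm ≈ 2(1.96 + 0.84)²/d² ≈ 15.7/d². At r = 0.3:
- Case A: raw change 15.7/0.034², over 13,000 per arm; log model 15.7/0.81², about 24.
- Case B: the signal is 0.689 and the SD of change 2.63, so d = 0.262 and n is about 229. The log model has residual SD 0.8 × √0.91 = 0.763, so d = 0.91 and n is about 19.

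These are population values, before any sampling error in a pilot SD.

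**The case against.** The strongest reply is that the plan says change, not raw change. A reader might infer that a raw-difference analysis has been chosen. The documents do not support that: scale and covariates are simply not stated. The sentence on change concerns the regression, in which the admission value is an obvious candidate covariate. The sentence on t-tests and Mann-Whitney does not say that they are applied to change, and Mann-Whitney on 4-week values would have 48-59% power in the table above. All of this stands, and it makes the defect an omission. It does not remove the point, because the plan equally permits the analysis with almost no power.

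Other stronger readings also fail:
- **That every blood marker is affected.** With little spread and a small peak, as assumed for fibrinogen and TNF-alpha, raw change detects a halving well.
- **That this is only a question of scale.** Raw change with the admission value as covariate matches or beats unadjusted log change in several scenarios, so baseline adjustment matters at least as much.
- **That the SD carried forward is biased low.** In small skewed samples the raw SD does tend to fall short: at log-SD 1.0, it is below the truth in 72% of samples of 30. The admission peak pushes the other way, by inflating the SD of change. The net direction is not established. What is clear is that this SD answers the wrong question.
- **That a real effect would be missed only because of this choice.** At 15 per arm it could well be missed after the fix too, and nothing in the documents supports a halving as the likely effect.

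**Conclusion.** The point holds as an under-specification with a large possible consequence, and should be corrected. If change in a skewed, peaked marker is formed by plain subtraction without adjustment, power for a true halving is about 4-15% (t-test) or 5-21% (Mann-Whitney) at 15 per arm. Log-scale regression on the admission value gives about 55-80% in the two main cases. Across the CRP- and IL-6-like profiles it gives 47-80%, with 47-66% for CRP, so the pilot remains modestly powered for that marker.

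Confidence is moderate. The timing and the missing specification come from the documents. Every marker level, spread and correlation is an assumption, as are the halving and complete paired samples. At 12 per arm, the first CRP-like profile (30 to 5, log-SD 1.1/1.0, r = 0.3) falls from 47% to 39%. The conclusion concerns chiefly CRP and IL-6. It does not extend to the immunoblot measures, for which nothing was computed.

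**What to change.** State in the SAP that, for CRP and IL-6:
- the log 4-week value is regressed on arm and log admission value;
- the result is the between-arm ratio of geometric means with a 95% CI;
- the residual log-scale SD, and not the SD of raw change, goes into the larger trial's sample size;
- Mann-Whitney is not applied to raw change.

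Use the same model for fibrinogen and TNF-alpha for consistency; little is gained or lost there. Report raw medians and quartiles at each visit as description.

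The cost is wording, with no new data or visits. A rule is needed for values below the assay limit, fixed before the data are seen. The model spends one degree of freedom on the covariate. The effect is read as a ratio and not an absolute difference, which is slightly less direct if the true effect is additive.
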